8.3.2 Regulatory Reporting for Studies Conducted Under DMID-Sponsored IND

Following notification from the site PI or appropriate sub-investigator, DMID, as the IND sponsor, will report any suspected unexpected serious adverse event (SUSAR) as an IND safety report to the FDA and will notify all participating site PIs (i.e., all PIs to whom the sponsor is providing drug under its IND(s) or under any PI's IND(s)) of potential serious risks from clinical studies or any other source, as soon as possible. DMID will report to the FDA any unexpected fatal or life-threatening suspected adverse reaction as soon as possible, but in no case later than 7 calendar days after the sponsor's initial receipt of the information. If the event is not fatal or life-threatening the IND safety report will be submitted within 15 calendar days after the sponsor determines that the information qualifies for reporting as specified in 21 CFR Part 312.32. Relevant follow up information to an IND safety report will be submitted as soon as the information is available. Upon request from FDA, DMID will submit to the FDA any additional data or information that the agency deems necessary, as soon as possible, but in no case later than 15 calendar days after receiving the request.

All SAEs that are not SUSARs will be reported to the FDA at least annually in a summary format.

8.3.3 Reporting of Pregnancy

Upon awareness, pregnancies occurring in subjects will be recorded on the Pregnancy Report eCRF. Subjects who become pregnant will be discontinued from further study procedures, but will be followed and recorded for safety until pregnancy outcome as per the protocol.

8.4 Type and Duration of Follow-up of Subjects after Adverse Events

AEs will be assessed, and followed from initial recognition of the AE through end of the protocol defined follow-up period.

SAEs will be followed up through resolution even if duration of follow-up goes beyond the protocol-defined follow-up period.

Resolution of an AE is defined as the return to pre-treatment status or stabilization of the condition with the expectation that it will remain chronic.

8.5 Procedures to be Followed in the Event of Abnormal Laboratory Test Values or Abnormal Clinical Findings

The site PI or appropriate sub-investigator is responsible for recording all AE/SAEs that are observed or reported during this trial, regardless of the relationship to the vaccine. AE/SAEs or abnormal clinical findings will be collected, assessed, documented, reported, and followed appropriately.

All subjects will be screened for GC and CT infection at all relevant mucosal sites with NAAT at screening (Visit 00A) and prior to rectal mucosal sampling procedures at Day 29 (Visit 04) and at the final study visit (Day 181 (Visit 08)). Female subjects will also be screened for *Trichomonas vaginalis* infection with NAAT at screening (Visit 00A). Subjects will also be screened for RPR at screening (Visit 00A), Day 29 (Visit 04) and Day 181 (Visit 08), as well as HIV-1/2 antibody (Visit 00A and 08). If a positive result on any of these screening tests occurs, the subject will be referred for appropriate follow-up and results reported as required by state law.

Safety labs will only be required at screening in the rectal biopsy cohort. Safety labs may be repeated during the study at the investigator's discretion as part of the assessment of abnormal clinical findings.

8.6 Halting Rules

8.6.1 Study Halting Criteria

The study will be halted for SMC review/recommendations if any of the following are reported:

- Any subject experiences an SAE after administration of study product that is considered related to study product.
- Any subject experiences an SAE after a study procedure that is considered related to the study procedure.
- An overall pattern of symptomatic, clinical, or laboratory events that the DMID Medical Monitor (MM) or SMC consider associated with the study product and that may appear minor in terms of individual events, but that may collectively represent a serious potential concern for safety.

If any of the halting rules are met, the study will not continue without a review of the safety data by and recommendation from the SMC before proceeding.

SMC retains the authority to suspend additional enrollment and administration of the study product during the entire study, as applicable.

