8.1.1 Adverse Events

ICH E6 defines an AE as any untoward medical occurrence in a patient or clinical investigation subject administered a pharmaceutical product regardless of its causal relationship to the study treatment. FDA defines an AE as any untoward medical occurrence associated with the use of a drug in humans, whether or not considered drug related.

An AE can therefore be any unfavorable and unintended sign (including an abnormal laboratory finding), symptom, or disease temporally associated with the use of medicinal (investigational) product. In addition, AEs specific to the rectal mucosal biopsy cohort will be collected prior to study drug administration and are defined as any unfavorable and unintended sign, symptom, or disease temporally associated with the rectal mucosal biopsy procedure. The occurrence of an AE may come to the attention of study personnel during study visits and interviews of a study recipient presenting for medical care, or upon review by a study monitor.

All AEs, including solicited local (injection site) and systemic (subjective and quantitative) reactions, will be captured on the appropriate eCRF. Information to be collected for AEs includes event description, date of onset, assessment of severity, relationship to study product and alternate etiology (assessed only by those with the training and authority to make a diagnosis and listed on the Form FDA 1572 as an investigator), date of resolution, seriousness and outcome. AEs occurring during the trial collection and reporting period will be documented appropriately regardless of relationship. AEs will be followed through resolution.

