8.1.1.1 Adverse Events Grading

All AEs (clinical symptoms) will be graded for severity and assessed for relationship to study product (see definitions). AEs characterized as intermittent require documentation of onset and duration of each episode. The start and stop date of each reported AE will be recorded on the

appropriate eCRF. Changes in the severity of an AE will be documented to allow an assessment of the duration of the event at each level of intensity.

Severity of Event:

AEs will be assessed by the investigator using a protocol-defined grading system (toxicity table included as an appendix). For events not included in the protocol-defined grading system, the following guidelines will be used to quantify severity:

- **Mild (Grade 1):** Events that are usually transient and may require only minimal or no treatment or therapeutic intervention and generally do not interfere with the subject's usual activities of daily living.
- **Moderate (Grade 2):** Events that are usually alleviated with additional specific therapeutic intervention. The event interferes with usual activities of daily living, causing discomfort but poses no significant or permanent risk of harm to the research participant.
- **Severe (Grade 3):** Events interrupt usual activities of daily living, or significantly affects clinical status, or may require intensive therapeutic intervention. Severe events are usually incapacitating.

Relationship to Study Product: The assessment of the AE's relationship to study product will be done by the licensed study physician indicated on the Form FDA 1572 and the assessment will be part of the documentation process. Whether the AE is related or not, is not a factor in determining what is or is not reported in this trial. If there is any doubt as to whether a clinical observation is an AE, the event should be reported.

In a clinical trial, the study product must always be suspect. The relationship to study product will be assessed for AEs using the terms related or not related:

- **Related** – There is a reasonable possibility that the study product caused the AE. Reasonable possibility means that there is evidence to suggest a causal relationship between the study product and the AE.
- **Not Related** – There is not a reasonable possibility that the administration of the study product caused the event.

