8.1.3 Serious Adverse Events

An AE or suspected adverse reaction is considered a SAE if, in the view of either the site PI or sponsor, it results in any of the following outcomes:

- Death,
- a life-threatening adverse event¹,
- inpatient hospitalization or prolongation of existing hospitalization,
- a persistent or significant incapacity or substantial disruption of the ability to conduct normal life functions, or
- a congenital anomaly/birth defect.
- Important medical events that may not result in death, be life-threatening, or require hospitalizations may be considered serious when, based upon appropriate medical judgment they may jeopardize the patient or subject and may require medical or surgical intervention to prevent one of the outcomes listed in this definition. Examples of such medical events include allergic bronchospasm requiring intensive treatment in an emergency room or at home, blood dyscrasias or convulsions that do not result in inpatient hospitalization, or the development of drug dependency or drug abuse.

¹ Life-threatening adverse event. An AE is considered “life-threatening” if, in the view of either the site principal investigator or sponsor, its occurrence places the patient or subject at immediate risk of death. It does not include an AE that, had it occurred in a more severe form, might have caused death.

SAEs will be:

- Assessed for severity and relationship to study product or procedure and alternate etiology (if not related to study product) by a licensed study physician listed on the Form FDA 1572 or by the Institution as the site PI or Sub-Investigator.
- Recorded on the appropriate SAE eCRF.

- Followed through resolution by a licensed study physician (for investigational new drug application (IND) studies, a physician listed on the Form FDA 1572 as the site PI or Sub-Investigator).
- Reviewed and evaluated by DMID, an Independent Safety Monitor (ISM) (as deemed necessary), or Safety Monitoring Committee (SMC) (periodic review unless related), and the IRB/IEC.

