8.2 Specification of Safety Parameters

Safety will be assessed by the frequency and severity of:

- Any AE related to 4CMenB immunization through the end of the study.
- Any AE related to rectal mucosal sampling procedures through the end of the study.
- Any SAEs through the end of the study.

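### The pattern halting criterion in Protocol 8.6.1 covers the study product but not study procedures, so a pattern of non-serious rectal biopsy complications meets no halting rule

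*Protocol*

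**What the plan says.** **Halting.** Protocol 8.6.1 lists three criteria. The first is a product-related SAE. The second is its counterpart for procedures: "Any subject experiences an SAE after a study procedure that is considered related to the study procedure". The third is for events that look minor one by one but may together be a serious concern, and it covers "An overall pattern of symptomatic, clinical, or laboratory events that the DMID Medical Monitor (MM) or SMC consider associated with the study product". If any criterion is met, "the study will not continue without a review of the safety data by and recommendation from the SMC before proceeding". The section adds that the SMC may suspend further enrollment and dosing; biopsies are not mentioned.

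**Safety parameters.** Protocol 8.2 (like 8.1) and SAP 9.3 list "Any AE related to rectal mucosal sampling procedures through the end of the study" among the things by which safety will be judged.

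**Attribution.** For AEs in general, 8.1.1 states: "Information to be collected for AEs includes event description, date of onset, assessment of severity, relationship to study product and alternate etiology". Section 8.1.1.1 gives the scale: "The relationship to study product will be assessed for AEs using the terms related or not related". For SAEs only, 8.1.3 is wider: "Assessed for severity and relationship to study product or procedure and alternate etiology".

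**Timing and display.** Protocol 8.1.1 says that "AEs specific to the rectal mucosal biopsy cohort will be collected prior to study drug administration". Section 10.5.4, however, bases the safety evaluation on events from the first dose of study product onward. Protocol 8.2.2 classes events after biopsy as unsolicited. The one biopsy row in SAP Table 51 counts them as solicited.

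**The concern.** The sponsor put procedures into the SAE criteria and left them out of the pattern criterion. The procedure in question is not trivial: about 20 participants each have two rigid-scope rectal biopsy sessions, the first on Day -28 to -14 and the second at Day 43. If minor complications began to accumulate, no criterion would impose the formal hold pending SMC review, and participants already biopsied once would still be due a second session.

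The reporting side has a related but separate weakness. A safety parameter is named, but the protocol does not say how a non-serious AE is to be judged related to the procedure. The stated analysis window also opens after half of the biopsies have been done. At stake are a small gap in the stopping rules and an under-specified summary of a named parameter. The immunogenicity results are not affected.

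**Working it through.** **Step 1. Which criterion could a pattern of non-serious biopsy AEs meet?**

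| Criterion in 8.6.1 | Needs an SAE? | Product | Procedure |
|---|---|---|---|
| 1. Product-related SAE | Yes | Yes | No |
| 2. Procedure-related SAE | Yes | No | Yes |
| 3. Pattern of events | No | Yes | No |

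No row combines non-serious events with procedures. Complications of the baseline biopsy precede any dose, so they cannot be product-associated. Those after Day 43 meet criterion 3 only if the Medical Monitor or SMC links them to the vaccine. This conclusion rests on 8.6.1 alone; it does not depend on how AEs are rated for relatedness. Section 8.6.2 does not fill the gap, because its individual rules withhold only the second vaccination.

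**Step 2. Can the named parameter be reported as specified?** Biopsy AEs are asked about and recorded at Visits 00C, 00P and 06P, so the events are captured. What is missing is:
- a written related/not-related rating against procedure for non-serious AEs;
- a window in 10.5.4 that includes the baseline biopsies;
- a consistent label, since the solicited list in 8.2.1 contains injection-site and systemic reactions only and Table 51 nonetheless calls biopsy AEs solicited.

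**Step 3. How many events are at issue?** Inputs:
- Biopsy cohort: 16 + 4 = 20 participants, two biopsies each (Protocol 3.1), so 20 × 2 = 40 procedures, 20 of them (50%) before any product.
- AE rate: 1.6% per procedure in the research-network summary cited in Protocol 2.3.1. Reproduced: 16 / 1,004 = 1.59%. That series used flexible sigmoidoscopy, had no SAEs, and 14 of its 16 related AEs were Grade 1.

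With X ~ Binomial(n, p) and procedures taken as independent, P(X ≥ 2) = 1 − (1−p)^n − n·p·(1−p)^(n−1).

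For n = 40, p = 0.016:
- Mean = 40 × 0.016 = 0.64.
- P(X ≥ 1) = 1 − 0.984^40 = 1 − 0.5246 = 0.475.
- P(X ≥ 2) = 1 − 0.5246 − 0.3412 = 0.134.
- P(X ≥ 3) = 0.026.

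For the 20 baseline biopsies alone: mean 0.32; P(X ≥ 2) = 1 − 0.7243 − 0.2355 = 0.040.

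The protocol says rigid-scope risk is presumably lower but unknown, so the rate is varied by assumption (n = 40):

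| Assumed rate | P(X ≥ 2) | P(X ≥ 3) |
|---|---|---|
| 0.8% (half) | 4.1% | – |
| 1.6% (cited) | 13.4% | 2.6% |
| 3.2% (double) | 36.8% | – |
| 5% | 60.1% | 32.3% |
| 10% | 92.0% | 77.7% |

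The last two rows show the situation a pattern rule exists for: a rate well above what was expected. All these are chances that events occur, not that a halt would be called, because the criterion has no count threshold. The named parameter also covers secretion sampling by anoscope, about 50 × 5 = 250 samplings, but the documents give no AE rate for it.

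**The case against.** The strongest reply is that the gap has little practical effect.

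- **The pattern criterion is itself a judgement.** It applies only if the Medical Monitor or SMC considers the events associated and collectively serious. The same bodies can already convene ad hoc under 8.7.2. This stands: the added words would not make several mild bleeds an automatic stop. They would add only the formal hold once that judgement is made.
- **Consequential complications are already covered.** One procedure-related SAE halts the study, and the SAE definition in 8.1.3 includes important medical events that may need intervention to avert a serious outcome. This stands too; what remains uncovered is mostly mild and self-limited.
- **Individuals are protected.** There is a call at 24 to 48 hours, a review of history, medications and vital signs before the Day 43 biopsy, and investigator withdrawal.
- **The site's record is good.** Protocol 2.3.1 reports more than 300 similar procedures with zero complications. The rule of three gives an upper bound of about 3/300 = 1%, at which P(X ≥ 2) in 40 is 1 − 0.6690 − 0.2703 = 6.1%. However, complications may be defined more narrowly than AEs.
- **The window may be less restrictive than 10.5.4 suggests.** SAP 9.3.2 says all reported AEs enter the summaries. That softens the point but leaves the two documents inconsistent.

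A reader might infer that non-serious biopsy AEs go unattributed, and that this is why no halting rule applies. The documents support neither. The visits record events as arising from the biopsy, 8.1.1 defines pre-dose biopsy AEs by their timing relative to the procedure, and Table 51 counts AEs due to it. The AE form itself is not in the documents and may already hold a procedure field. The halting gap comes only from the wording of the pattern criterion.

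**Conclusion.** The point holds as a narrow one. On the text of 8.6.1, a pattern of non-serious biopsy complications meets no halting rule, and the discretionary routes that remain carry no formal hold and no stated power over biopsies. Separately, reporting of a named safety parameter is under-specified in the attribution rating, the start of the window and the Table 51 label.

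It should not be read as an absence of safeguards; those listed above remain in place. The expected gain is small: 0.64 biopsy AEs across the study at the cited rate, and two or more in about one study in seven (13.4%). These figures assume 40 completed, independent biopsies and carry a flexible-scope rate over to a rigid scope. The wording gap itself rests on no figure. This is an improvement to consider, worthwhile because it costs almost nothing.

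**What to change.** 1. In Protocol 8.6.1, extend the pattern criterion so that it covers events associated with the study product *or a study procedure*.
2. In Protocol 10.5.4, start the AE window at the baseline biopsy for the biopsy cohort, and relabel the biopsy row of SAP Table 51 as unsolicited. Table 51 uses the Safety Population, which requires a dose, so anyone biopsied but never dosed would still be missed; a short listing would cover them.
3. In Protocol 8.1.1 and 8.1.1.1, state that non-serious AEs are also judged for relationship to study procedure, as 8.1.3 already does for SAEs. Add a field to the AE form only if it lacks one.

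The cost is a few words in four protocol sections, one table label and at most one form field. If a field is added after AEs have been entered, it must be back-filled. Visits, sample size and procedures do not change.

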8.6.2 Individual Halting Criteria

A subject will be discontinued from second vaccination if:

- Subject develops a new medical condition or medication change for which continued participation, in the opinion of the investigator, would pose a risk to the subject
- Subject is no longer willing and/or able to adhere to study restrictions outlined in the Inclusion and Exclusion Criteria
- Subject has a fever (defined as an oral temperature $\geq 38.0^{\circ}\text{C}$) or an acute illness at the time of boost vaccination administration. The next study vaccination can be deferred until

the fever or illness resolves or only minor residual symptoms remain, that in the opinion of the investigator, will not interfere with the ability to assess safety parameters as required by the protocol, provided that the boost is given within the protocol-defined study window.

- Subject has received COVID-19 vaccine <14 days prior to scheduled dose #2. The next study vaccination can be deferred until at least 14 days elapse from the time of any COVID-19 vaccination, if in the opinion of the investigator, will not interfere with study assessments as required by the protocol, provided that the boost is given within the protocol-defined study window.
- Permission to administer vaccination outside the protocol-defined study window must be obtained from DMID Medical Officer.

Note: In case the boost vaccination is postponed, the timing of the safety/immunogenicity visits post-boost will be planned relative to actual vaccination day.

8.7 Safety Oversight

8.7.1 Independent Safety Monitor (ISM)

For this clinical trial an ISM is not required. However, **upon DMID Medical Monitor request,** the PI will identify a physician with relevant expertise, to act as a Secondary Medical Assessor (SMA). The SMA will examine a subject and/or medical records and provide a medical assessment (or second medical opinion) to the DMID of the safety event in question. The PI will send to the DMID MM, a summary of the event and include the PI and SMA assessments.

Note: In the case that DMID has requested this type of evaluation multiple times, DMID may request the site(s) identify an ISM to assist DMID with safety oversight.

8.7.2 Safety Monitoring Committee (SMC)

This clinical study will utilize an SMC, which is an independent group of experts that advises the DMID. The primary responsibility of the SMC is to monitor subject safety. The SMC is external to the DMID and comprises at least 3 voting members. A simple majority will be considered a quorum for voting purposes. The SMC will consist of members with appropriate expertise to contribute to the interpretation of the data from this trial. Its activities will be delineated in a SMC charter that will describe the membership, responsibilities, and the scope and frequency of data reviews. The SMC will operate on a conflict-free basis independently of the study team. The

DMID or the SMC may convene ad hoc meetings of the SMC according to protocol criteria or if there are concerns that arise during the study.

As defined in the charter, the SMC will review data at specified times during the course of the study for subject and overall study progress, and will conduct ad hoc reviews as appropriate when a halting rule is met or for immediate concerns regarding observations during this study.

The SMC will convene for the following meetings: Organizational meeting, scheduled data review meetings, ad hoc meetings for a specific safety concern or issue, final meeting.

9 HUMAN SUBJECTS PROTECTION

9.1 Institutional Review Board/Independent Ethics Committee

Each site PI will obtain IRB approval for this protocol to be conducted at his/her research site(s), and send supporting documentation to the DMID before initiating recruitment of subjects. The investigator will submit applicable information to the IRB/IEC on which it relies for the review, to conduct the review in accordance with 45 CFR 46, ICH E6 GCP, and as applicable, 21 CFR 56 (Institutional Review Boards) and 21 CFR 50 (Protection of Human Subjects), other federal, state, and local regulations. The IRB/IEC must be registered with OHRP as applicable to the research. DMID must receive the documentation that verifies IRB/IEC-approval for this protocol, associated informed consent documents, and upon request any recruitment material and handouts or surveys intended for the subjects, prior to the recruitment and enrollment of subjects.

Any amendments to the protocol or consent materials will be approved by the IRB/IEC before they are implemented. IRB/IEC review and approval will occur at least annually throughout the enrollment and follow-up of subjects, and may cease if annual review is no longer required by applicable regulations and the IRB/IEC. The investigator will notify the IRB/IEC of deviations from the protocol and reportable SAEs, as applicable to the IRB/IEC policy.

The institution engaged in this research will hold a current FWA issued by the Office of OHRP for federally funded research.

